2. OVERVIEW OF STUDY TREATMENT AND STUDY DESIGN

2.1 Study Treatment

SQ3370 is a novel Investigational Product that enables local targeting and activation of a cytotoxic prodrug without the need for specific molecular biomarkers. SQ3370 utilizes Shasqi's proprietary Click Activated Prodrugs Against Cancer (CAPAC™) platform where mutually reactive click chemistry groups release doxorubicin (Dox) at the tumor site minimizing systemic exposure.

The therapeutic goal of SQ3370 is to enhance the antitumor efficacy of doxorubicin by increasing its concentration at a specific tumor site while minimizing its systemic toxicity.

The SQ3370 Investigational Product consists of 2 components:

- (1) Intratumoral injection of a prodrug activating biopolymer (SQL70: 10 mL or 20 mL).
- (2) five consecutive days of intravenous (IV) infusions of a trans-cyclooctene (TCO)-modified prodrug of Dox with attenuated cytotoxic activity (SQP33) for a 21-day cycle. In and around the tumor site, SQL70 biopolymer selectively and rapidly captures SQP33 prodrug via an irreversible covalent reaction between tetrazine and TCO (biorthogonal chemical groups), followed by local release of active Dox. SQP33 is the active component.

An individual cycle of treatment is defined as a 3-week (21-day) period where SQL70 biopolymer is injected into lesion(s) on Day 1 followed by 5 consecutive daily infusions of SQP33 prodrug (Day 1 – Day 5).

The SQL70 biopolymer and SQP33 prodrug are packaged separately given that the number of SQP33 prodrug vials needed will vary by subject/cohort dose level.

2.2 Experimental Design

This multicenter, Phase 1/2a, first-in-human, single-arm, open-label, dose-escalation study will be conducted in two stages. This includes a dose escalation stage to evaluate the safety and tolerability, PK, and preliminary efficacy of SQ3370 in subjects with locally advanced or metastatic solid tumors for which an anthracycline-containing regimen is appropriate and who have an injectable tumor. The dose-escalation portion of the study will be used to determine the maximum tolerated dose (MTD) and/or recommended Phase 2 dose (RP2D) of SQ3370. The SQL70 biopolymer will be administered intra and/or peritumorally at a dose of either 10 mL or 20 mL injection volume. The 10 mL dose is intended for a single lesion or cluster of lesions, and the 20 mL dose is for concurrent treatment of 2 lesions, or for a single larger lesion.

2.2.1 Dose Escalation Cohorts Phase 1

Subjects enrolled into this study will be divided into two groups:

[figure not shown]
Group 1- 10 mL SQL70 Biopolymer (post-Cycle 1) Cohort: Subjects that will have one lesion injected during cycle 1 (10 mL injection volume) with the possibility of additional lesions injected in later cycles. This group consists of an accelerated dose-escalation with 1 subject per dose (stage 1) followed by a 3+3 (Rolling 6 design where between 3-6 subjects may be enrolled concurrently) (stage 2) beginning with the highest dose evaluated during stage 1.

Group 2- 20 mL SQL70 Biopolymer (from Cycle 1) Cohort: Subjects that may have one or more lesions injected during cycle 1 (20 mL injection volume) and consists of a cohort of subjects to be evaluated following administration of 20 mL of SQL70 biopolymer in one or two lesions starting at Cycle 1. This cohort of subjects will be enrolled at an initial dose level of SQP33 protodrug that is lower than the dose level being evaluated in the standard dose escalation (Group 1) at the time of initiation of this cohort. This 20 mL SQL70 biopolymer (from cycle 1) cohort will follow the same 3+3 (Rolling 6) escalation design as described below. The SRC will decide if another cohort of subjects should be enrolled at a higher SQP33 protodrug dose with the same 20 mL SQL70 biopolymer volume.

2.2.2 Dose Escalation Methods

The dose escalation portion of the study comprises an initial period of accelerated titration cohorts (Stage 1) followed by 3+3 (Rolling 6) design (Stage 2). Subjects will receive specific dose levels of SQP33 protodrug assigned according to the dose escalation design described below. This design is appropriate for cytotoxic therapies to minimize subject dosing at subtherapeutic levels. Additionally, two Phase 1 clinical trials with similar aminoglycoside-modified Dox-based drugs used similar accelerated dosing protocols and dose adjustment criteria (DiPaola 2002; Schöffski 2017).

Schema of Single Patient Accelerated Dose Escalation Followed by 3+3 Design with Modified Fibonacci Dose Escalation

The SRC will review all available safety data at the completion of Cycle 1 for each of the dose escalation cohorts and the cohort receiving 20 mL SQL70 biopolymer from Cycle 1 to

evaluate possible DLTs, recommend whether more subjects should be enrolled at a given dose level / cohort, and recommend whether to dose escalate or to stop enrollment based on the definition of DLTs in addition to its members' best clinical judgement.

Stage 1: Accelerated Titration

In the absence of AEs considered by the SRC to be clinically relevant during any cycle, the SQP33 protodrug accelerated dose titration stage includes 1 subject enrolled per cohort with a doubling of the SQP33 protodrug dose level between cohorts.

Escalation transitions to a standard 3+3 modified Fibonacci design (see below) upon identification during the DLT period of either:

- a DLT, or
- any Grade ≥ 2 AE considered to be at least possibly related to study drug

Stage 2: 3+3 (Rolling 6) Design

The 3+3 (Rolling 6) design stage includes 3-6 subjects enrolled per cohort and utilizes a modified Fibonacci scale to determine the dose level increase and minimum number of subjects enrolled per dose level (Table 3). In the Rolling 6 design, a minimum of three, and up to six subjects may be concurrently enrolled at each dose level in the study prior to convening the SRC to evaluate the safety and tolerability of the dose level.

The first cohort of subjects enrolled in the Stage 2 dose escalation portion will be at the same dose level as the highest evaluated Stage 1 dose level. This will ensure that any dose level resulting in a DLT is tested in additional subjects prior to continued dose escalation. If 2 subjects experience 1 or more DLTs in any cohort, no additional subjects will be enrolled at that dose level and further subjects will be enrolled at a lower dose level.

Decisions as to whether to allow additional enrollment beyond the minimum of three into a cohort or pause accrual for that cohort will be made by the Sponsor based on available data (i.e., the Sponsor will inform sites if a cohort is still open for additional accrual or if the cohort is closed to accruals). Dose level assignments are based on the number of participants currently enrolled in the cohort, the number of DLTs observed, the number of participants who have not completed the DLT period, general tolerability observed, and any available PK data.

Modified Fibonacci Dose Escalation Scale (Stage 2)

| Number of Patients with DLTs in a Dose Level | Action |
|--|--|
| 0 patients with DLTs across 3-6 patients in a dose level | Enroll an additional 3 to 6 patients at a dose level escalation of 50% |
| 1 patient with a DLT across 3-5 patients in a dose level | 
 Enroll additional patients (for a total of 6 at this dose level) 
 If no patients experience additional DLTs across the 6 total patients, then enroll 3 patients at a dose level escalation of 33% If a second patient experiences a DLT, see the below (≥ 2 DLTs across ≥ 3 patients at a dose level) |
| ≥ 2 patients with DLTs in a dose level | 
 Dose escalation will be stopped. An intermediate dose level may be explored that is not higher than the MAD |

Finally, a determination of the recommended Phase 2 dose(s) (RP2D) will be determined based on all available dose escalation data. This includes PK/PD analysis, tolerability that will include the incidence and severity of DLTs, other AEs and the evidence for biological activity at each dose level tested. The RP2D will be defined by an SQP33 protodrug dose and a SQL70 biopolymer volume and carried forward into the Phase 2a dose expansion phase of this study.

2.3 Phase 2a: Expansion Groups

Subjects will be enrolled in the Phase 2a expansion groups to study the preliminary activity and gain additional SQ3370 safety data, dosing schedules, as well as PK and immune changes in blood and tumor tissue.

A separate SAP will be written for the Phase 2a Expansion Group part of this study.

3. STUDY OBJECTIVES AND ENDPOINTS

3.1 Study Objectives

3.1.1 Dose Escalation Primary Objectives

Assess the safety and tolerability of SQ3370 treatment, including determination of the maximum tolerated dose (MTD) and/or recommended Phase 2 dose (RP2D) of SQP33 protodrug administered with 10 mL and/or 20 mL of SQL70 biopolymer

3.1.2 Dose Escalation Secondary Objectives

- Characterize the PK profile of SQP33 protodrug and active doxorubicin (Dox) following SQ3370 treatment

- Assess preliminary signals of SQ3370 anti-tumor activity

3.1.3 Dose Escalation Exploratory Objectives

- Assess the concentration of active Dox and SQP33 protodrug following SQ3370 treatment at the local site through analysis of tumor biopsies
- Assess immune response through biomarker analysis of tumor biopsies and peripheral blood specimens
- To study the pharmacodynamics (PD) of SQ3370 therapy by assessing potential biomarkers in archival tumor tissue and peripheral blood.

3.2 Study Endpoints

3.2.1 Safety Endpoints

Frequency of adverse events (AEs), Serious Adverse Events (SAEs) and dose-limiting toxicities (DLTs), as well as changes from baseline in vital signs, clinical laboratory parameters, physical examination findings, ECHO/MUGA, and electrocardiogram (ECG) results.

3.2.2 Efficacy Endpoints

- Objective response rate (ORR) per Response Evaluation Criteria in Solid Tumors (RECIST) v1.1.
- Duration of Response (DoR) in target lesion(s) (including both injected and, if available, non-injected tumors).
- Disease Control Rate (DCR)
- Duration of Stable Disease
- Change in size of target lesion(s) (including both injected and, if available, non-injected tumors).

3.2.3 Pharmacokinetic (PK) Endpoints

Plasma concentration and pharmacokinetics (PK) parameters for SQP33 protodrug and active Dox following SQ3370 treatment.

3.2.4 Exploratory Endpoints

- Assess the presence of SQP33 protodrug and active Dox in tumor tissue.
- Characterize immune response in blood and tumor tissue over time following treatment with SQ3370.

4. SAMPLE SIZE JUSTIFICATION

The dose escalation portion of the study is based on Design 4 in Simon 1997 and comprises an initial period of accelerated titration cohorts (Stage 1) followed by 3+3 (Rolling 6) cohorts (Stage 2). No formal sample size calculations were used to determine sample sizes. Total enrollment is not predefined and is dependent upon the Dose Limiting Toxicities (DLT) observed and the number of escalation cohorts.

The following sample sizes are planned:

- Accelerated Dose-Escalation: n=1 subject per cohort
- 3+3 Dose Escalation: n=3 to 6 subjects per cohort

Additional subjects may be enrolled for the cohorts having multiple lesions injected during cycle 1 (3+3 cohorts and any additional cohorts recommended by the SRC).

Subjects may be replaced if they were enrolled into the study but did not receive the intended doses of study drug during Cycle 1 for reasons other than adverse events (AEs).

5. RANDOMIZATION, BLINDING, AND REPLACEMENT OF SUBJECTS

This is an open-label study with the identity of the treatment known to the subjects, Investigators, and Sponsor; therefore, no randomization or blinding procedures will be performed.

All subjects will receive SQ3370 treatment according to the dose cohort in which they are enrolled. Subjects will be enrolled into open dosing cohorts from all participating centers.

Subjects who are lost to follow-up or withdraw consent for study participation prior to administration of study drug may be replaced, at sponsor's discretion.

6. DEFINITIONS OF SUBJECT POPULATIONS TO BE ANALYZED

This study will have six analysis populations:

- Enrolled: All subjects who sign consent.
- Treated / Full Analysis Set: All subjects who receive at least 1 dose of SQL70 biopolymer and 1 dose of SQP33 protodrug.
- Safety Analysis Set: All subjects who received at least 1 dose of SQL70 biopolymer and/or SQP33 protodrug.

- Efficacy Evaluable Analysis Set: All subjects who receive at least 1 dose of SQL70 biopolymer and 1 dose of SQP33 protodrug and undergo at least 1 post baseline tumor evaluation
- PK Analysis Set: All subjects in the Safety Population who have the necessary Day 1 and on-study measurements to provide interpretable results for the specific parameters of interest.
- Biomarker Analysis Set: All subjects with available biomarker data.

7. PLANNED ANALYSES

7.1 Interim Analysis

There are no formal interim analyses planned for this Phase 1 open-label study. All subjects will receive SQ3370 treatment according to the dose cohort in which they are enrolled. A Safety Review Committee (SRC) will review the data in an ongoing manner and include the study team led by the medial monitor, and the active Investigator(s). The SRC will review all available safety data at the completion of Cycle 1 for each cohort to evaluate possible DLTs, recommend whether more subjects should be enrolled at a given dose level / cohort, and whether to dose escalate or to stop enrollment based on the definition of DLTs in addition to its members' best clinical judgement and will provide recommendations to the sponsor.

With agreement from the sponsor, the dose escalation scheme may be modified (e.g., smaller increases or decreases in dose may be permitted, infusion timing, duration, or schedule may be modified) based on available PK and pharmacodynamic data, and/or the timing and severity of AEs observed. Changes that can only be made with a protocol amendment will include:

- Dose level escalations that are increased by larger increments than the scheme in the protocol
- Administration of more than 5 SQP33 infusions per cycle
- Administration of more than 20 mL of SQL70 biopolymer per cycle

Summary tables and listings will be generated after the Dose Escalation phase has been completed.

7.2 Final Analysis

The final tables, listings, graphs, and data analysis will be conducted once all study participants have completed the study (dose escalation phase) and the clinical database has been locked.

8. DATA PRESENTATION AND HANDLING

8.1 Table and Individual Subject Data Listing Considerations

Summary tables and listings will be prepared according to ICH Guideline E3 (as appropriate for a Phase I study).

In general, summary tables will be organized with respect to:

- SQL70 biopolymer dose (10 mL and 20 mL)
- SQP33 prodrug Dose Escalation: lowest dose to highest dose
- Total per SQL70 biopolymer dose

Row entries in post text tables are made only if data exists for at least one subject (e.g., a row with all zeros will not appear). The only exception to this rule will apply to tables that summarize the study termination status of subjects (e.g., reasons for not completing the study). In this case, zeros will appear for study termination reasons that no subject satisfied. The summary tables will clearly indicate the number of subjects to which the data apply and unknown or not performed are distinguished from missing data.

Summary tables for any concomitant medications will be coded according to the World Health Organization (WHO) Drug dictionary September 2020. Adverse event preferred terms and body/organ systems and medical history conditions will be coded using the Medical Dictionary for Regulatory Activities (MedDRA®) dictionary Version 24.1 (or later).

Listings will also be sorted by dose cohort (where applicable) and subject number. Listings will also include visit number, visit date/time and days relative to the initiation of study treatment.

In general, missing data will not be imputed unless otherwise specified. Any imputed or derived data will be flagged in the individual subject data listings. Imputed data will not be incorporated into any raw or primary datasets. These data will be retained in derived analysis datasets.

8.2 Format Considerations

The tables, figures and listings will be numbered using a decimal system to reflect main levels of unique tables and listings and sub-levels of replicate tables and listings with two digits per level (e.g., Table XX.YY.ZZ.).

1. The first level number will be consistent with the corresponding Clinical Study Report (CSR) appendix in which the tables or listings will appear. For example, the post text tables will appear in Appendix 14 (and will be numbered 14.XX.YY) and the

individual subject data listings will appear in Appendix 16 (and will be numbered 16.XX.YY). The subject disposition table will be first in the first section of the report and will be numbered Table 14.1. The supportive subject data listing will be Listing 16.1. Any subset table will have the number Table 14.1.2, etc.

2. Table numbering will follow ICH E3 for Phase I CSRs. Subject disposition, baseline and demography and prior and concomitant medications tables should appear as the second level number (Table 14.1 series). Efficacy tables will occupy the next sub-level (Table 14.2 series – 14.2.1, 14.2.2 and 14.2.3, respectively). Safety tables will follow next (Table 14.3 series). Similar conventions will be applied to the subject data listings.
3. Each table and listing title will be complete, accurate and concise. The last line of the title will provide the analysis group being summarized (e.g., Safety Population or Efficacy Evaluable Population).
4. If possible, variables being summarized, and statistics reported will appear in the left most column of a table. The next columns for (dose level) should report the data from left to right for the SQ3370 treatment dose cohort (from low to high).

8.3 Data Management

All data will be recorded by the site in individual source documents. An eCRF will be created by the data management vendor (Novotech) for recording of the required data in the study database. All eCRF information is to be filled in by site staff. If an item is not available or is not applicable, this fact should be indicated. Blank spaces should not be present unless otherwise directed.

The study monitor will perform source data verification of data entered into the eCRF and raise queries for correction by the site. The data entered into the eCRF will be subject to data validation checks for consistency and completeness by the data management vendor and sponsor. Data queries will then be generated and sent to the investigational site for response before the database is locked and released for statistical analysis.

Database build, AE coding, medication coding, data cleaning will be conducted according to the Novotech (vendor clinical research organization) Data Management Plan for this specific study.

Derived datasets (including SDTM and ADaM) will be created using SAS® software. Data analyses and summary tables will be generated using the currently supported version at the time of data analysis (currently version 9.4).

8.4 Data Presentation Conventions

Continuous safety variables (e.g., clinical laboratory values and vital signs) will be listed to the same precision as the source data. Derived variables will be calculated and listed using the same precision as the value(s) from which they were derived.

For the tabular reporting of descriptive statistics:

- Continuous variables: the same number of decimal places as in the raw data will be presented when reporting minimum and maximum, 1 more decimal place than in the raw data will be presented when reporting mean and median, and 2 more decimal places than in the raw data will be presented when reporting SD.
- Categorical/discrete variables: the frequency count and the percentage (of available data) for each class of the variable will be presented and will be displayed in the form XX (XX.X%) where the percentage is in the parentheses. All percentages will be presented to 1 decimal place, unless otherwise specified. Percentages equal to 100 will be reported as 100% and percentages will not be presented for zero frequencies. Unless otherwise specified, percentages will be calculated based on the number of subjects specified by the appropriate population definition.
- Date variables: formatted as DDMMYY for presentation. Time will be formatted in military time as HH:MM for presentation.

Extra measurements (such as unscheduled or repeat assessments) will not be included in summary tables but will be included in subject listings. They will be used in summary tables which are not 'time specific', for example, summaries of minimum maximum, first, last, average post dose values.

All tables, listings, figures will be produced in landscape orientation using Arial 9-point font. Output files will be created in rich text file (RTF) format.

Missing or invalid data will be generally treated as missing, not imputed, unless otherwise stated (see Section 9.5).

The table, figures and listing shells and table of contents as part of this SAP provide the expected layout and titles of the tables, listings, and figures. Any changes to format, layout, titles, numbering, etc. will not necessitate a revision to the SAP, nor will it be considered a deviation from planned analyses. Only true differences in the analysis methods or data handling (e.g., change in the population used, change from statistical method/assumption listed, transformation of data type [e.g., continuous data transformed to categorical], exclusion of planned analysis, etc.) or additional unplanned analyses will necessitate a

revision to this SAP. The appropriate listings supporting the tables will be included and are not specified in the individual sections throughout the document.

8.5 Treatment Comparisons

The following labels for dose level will be used on all tabulations, in the following order:

| Dose Escalation: 10mL SQL70 Biopolymer + SQP33 Dox Equiv. Dose (mg/m2) | | | | | | | | | |
|--|-----------------|-----------------|----------------|--------------|--------------|--------------|---------------|---------------|-----------------|
| 0.38x (N=00) | 0.76x (N=00) | 1.53x (N=00) | 2.8x (N=00) | 4x (N=00) | 6x (N=00) | 8x (N=00) | 12x (N=00) | 15x (N=00) | Total (N=00) |

| Dose Escalation: 20mL SQL70 Biopolymer + SQP33 Dox Equiv. Dose (mg/m2) | | |
|--|--------------|-----------------|
| 4x (N=00) | 6x (N=00) | Total (N=00) |

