3.1.1. Phase 1 Dose Escalation

Patients will receive specific dose levels of SQP33 protodrug, assigned according to the dose escalation design described in section [3.2 Phase 1 Dose Escalation](#).

20 mL SQL70 Biopolymer (post-Cycle 1) Cohort:

Patients *on treatment* who attain at least a 30% reduction in injected tumor size or have a tumor that is no longer injectable may have a second lesion injected with an additional 10 mL of SQL70 biopolymer, thereby receiving a total of 20 mL of SQL70 biopolymer (see section [3.1.4.4 Phase 1: 20 mL SQL70 Biopolymer \(post-Cycle 1\) Cohort](#)).

20 mL SQL70 Biopolymer (from Cycle 1) Cohort:

To evaluate the administration of 20 mL of SQL70 biopolymer in one or two lesions starting at Cycle 1, patients will be enrolled in a separate cohort at a dose level of SQP33 protodrug that is lower than the current dose level being evaluated.

Also see the [Schedule of Assessments Appendix G](#).

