3.1.4.4. Phase 1: 20 mL SQL70 Biopolymer (post-Cycle 1) Cohort

For patients who have received treatment cycles with 10 mL of SQL70 biopolymer in Phase 1 Dose Escalation:

If the injected lesion is considered no longer injectable by the Investigator (see section [3.1.4.3 Treatment Duration](#)) then the area of the tumor bed, if possible, should be treated for two additional cycles. Additional lesion(s) may be treated with a further 10 mL of SQL70 biopolymer (for a total of 20 mL SQL70 biopolymer maximum administered per cycle) as considered appropriate by the investigator.

The administration of the additional 10 mL SQL70 biopolymer for patients already on study as described above is a separate group of patients from the cohort that will receive 20 mL SQL70 biopolymer beginning at Cycle 1 (see section [3.2.3 Phase 1: 20 mL SQL70 Biopolymer \(from Cycle 1\) Cohort](#)).

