3.2.5. Recommended Phase 2 Dose

A determination of the RP2D will be based on the safety and tolerability from every cycle of treatment, not just Cycle 1. The RP2D will be determined based on all available data, including PK/PD analysis, tolerability that will include the incidence and severity of DLTs, other AEs and the evidence for biological activity at each dose level tested. The RP2D will be defined by an SQP33 protodrug dose and a SQL70 biopolymer volume.

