10.8 Study Drug Administration: Exposure and Modifications

Group 1 (10 mL SQP70): SQL70 biopolymer will be administered intra and/or peritumorally at a fixed 10 mL injection volume. During cycle 1, a single lesion (or regional cluster of lesions) will be injected on Day 1. For later cycles, Subjects on treatment who attain at least a 30% reduction in injected tumor size or have a tumor that is no longer injectable may have a second lesion injected with an additional 10 mL of SQL70 biopolymer.

The starting daily dose of SQP33 protodrug is 8 mg/m²/day (5.72 mg/m²/day Doxorubicin Molar Equivalent Dose (Dox Eq)) for the first accelerated dose cohort. SQP33 protodrug infusions are given daily on Day 1 through Day 5. The starting total dose per cycle of SQP33 will be 40 mg/m²/cycle (28.6 mg/m²/cycle Dox Eq). Higher doses will be converted to their doxorubicin hydrochloride molar equivalent (1 g of SQP33 protodrug is equivalent to 0.7153 g of doxorubicin hydrochloride). Dose escalation during stages 1 and 2 will take place after the SRC reviews Cycle 1 safety data.

Group 2 (20 mL SQL70): consists of a cohort of subjects to be evaluated following administration of 20 mL of SQL70 biopolymer in one or two lesions starting at Cycle 1. This cohort of subjects will be enrolled at an initial dose level of SQP33 protodrug that is lower than the dose level being evaluated in the standard dose escalation (Group 1) at the time of initiation of this cohort. This 20 mL SQL70 biopolymer (from cycle 1) cohort will follow the same 3+3 (Rolling 6) escalation design as used for the subjects described previously. The SRC will decide if another cohort of subjects should be enrolled at a higher SQP33 protodrug dose with the same 20 mL SQL70 biopolymer volume.

Study treatment (SQP33 and SQL70) received will be summarized as described below:

Study Drug Administration (Exposure):

- Number of cycles
- Duration of Therapy
- Average Duration of SQP33 Infusions
- Total SQP33 Cumulative Dose (mg/m²)
- Total SQL70 Cumulative Dose (mg/m²)
- Total Doxorubicin Equivalent Cumulative Dose (mg/m²)
- Highest SQP33 dose administered
- Highest Doxorubicin Equivalent dose administered

Dose Modifications:

1. SQL70 Biopolymer
 - a. Injection interruption
 - b. Dose increase of biopolymer (10 mL to 20 mL)

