12.1 Treatment Emergent Adverse Events

Treatment-emergent adverse events (TEAEs) are defined as all AEs that begin on or after the date of the first administration of study drug. Related AEs are those reported as possibly related to SQL70 biopolymer, related to SPQ33 protodrug, and related to SQ3370 (both SQL70 and SQP33). The verbatim terms of the TEAEs will be coded to preferred terms (PT) and system organ classes (SOC) per the Medical Dictionary for Regulatory Activities (MedDRA®) Version 24.1.

All reported AEs (including non-TEAEs) will be listed, documenting all information collected on the eCRF including verbatim term, MedDRA preferred term, MedDRA system organ class, start date, stop date, severity and relationship to SQ3370 treatment, relationship to SQL70 biopolymer, relationship to SQP33 protodrug, action taken, and outcome.

The TEAEs will be graded by the Investigator in terms of:

- Severity graded 1-5 according to CTCAE v5.0:
 - 1=Mild, 2=Moderate, 3=Severe, 4= Life Threatening, 5=Fatal.
- Relation to SQ3370:
 - ‘Related’ includes events where the causality was reported as related to SQL70 biopolymer, related to SPQ33 protodrug, related to SQ3370 treatment (both SQL70 and SQP33), or where the relationship was not reported on the eCRF.
 - ‘Not Related’ includes events where the study drug causality was reported ‘Not Related’ on the eCRF.

All TEAE summary tables will be presented with the number and percentages of subjects in the Safety population. Incidence rates of treatment-emergent adverse events (TEAEs) will be summarized within each dose level at the Medical Dictionary for Regulatory Activities (MedDRA) primary system organ class levels and preferred term. Subjects may be counted under multiple system organ class (SOC) and preferred terms (PT), but for each SOC and PT category, subjects are only counted once. If a subject has the same AE on multiple

occasions, the highest severity grade (fatal > life threatening > severe > moderate > mild) or drug relationship (related > not related) recorded for the event will be summarized.

This list includes:

- All TEAEs
- All TEAEs graded severity
- All Related TEAEs to SQ3370 treatment
- All Related TEAEs to SQ3370 treatment graded by severity
- All Related TEAEs to SQL70 biopolymer
- All Related TEAEs to SQL70 biopolymer graded by severity
- All Related TEAEs to SQP33 protodrug
- All Related TEAEs to SQP33 protodrug graded by severity
- Serious TEAEs
- Adverse Event of Special Interest (AESI)

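### Phase 1 safety tables are labelled by SQL70 volume but have no rule for patients who move from 10 mL to 20 mL after Cycle 1, so any toxicity arising on 20 mL would be reported under 10 mL

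*SAP*

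**What the plan says.** **The switch is allowed.** Under Protocol 3.1.1, a patient whose injected tumor has shrunk by at least 30% or can no longer be injected "may have a second lesion injected with an additional 10 mL of SQL70 biopolymer, thereby receiving a total of 20 mL of SQL70 biopolymer". Protocol 3.1.4.4 heads these patients as a 20 mL (post-Cycle 1) cohort and says that this additional dosing "is a separate group of patients from the cohort that will receive 20 mL SQL70 biopolymer beginning at Cycle 1".

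**The Phase 1 SAP keeps them with 10 mL.** Section 2.2.1 names Group 1 the 10 mL (post-Cycle 1) cohort and defines it as "Subjects that will have one lesion injected during cycle 1 (10 mL injection volume) with the possibility of additional lesions injected in later cycles". Section 10.8 repeats, under the 10 mL group, that patients "may have a second lesion injected with an additional 10 mL of SQL70 biopolymer". Section 16 lists no change from the protocol.

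**The tables are fixed by volume.** Section 8.1 organizes them by SQL70 dose, then SQP33 dose, with a total for each volume. Section 8.5 states: "The following labels for dose level will be used on all tabulations, in the following order". It then gives nine 10 mL levels (0.38x to 15x) and two 20 mL levels (4x and 6x).

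**Safety is summarized over all cycles.** Section 12.1 states: "Incidence rates of treatment-emergent adverse events (TEAEs) will be summarized within each dose level". Section 12 counts each preferred term once per patient at its highest grade. Sections 12.7.2 to 12.7.4 use first, last, minimum, maximum and average post-baseline laboratory values. The move from 10 mL to 20 mL appears only as a dose-modification item in section 10.8.

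**Volume is part of the RP2D.** Protocol 3.2.5 says: "A determination of the RP2D will be based on the safety and tolerability from every cycle of treatment, not just Cycle 1". The same section defines the RP2D by an SQP33 dose together with an SQL70 volume.

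**The concern.** A column headed 10 mL is read as experience on 10 mL. For a patient who switches, it would also hold everything that happens on 20 mL. A post-switch worsening would replace the earlier grade in the same column, and a post-switch nadir would become that patient's minimum value.

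Two things are at stake. First, the 10 mL safety summaries may not describe 10 mL alone, although volume is half of the RP2D definition and all cycles count. Second, 20 mL experience may be hidden. The cohort given 20 mL from Cycle 1 was treated only at 4x and 6x, while section 10.8 of the Phase 2a SAP gives Group 1 as 20 mL with 12x. Any patient who switched above 6x would supply Phase 1 data on 20 mL at those levels, and the tables have no 20 mL column to show it. This is a point about what a reader can see, not about which volume or dose is right.

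**Working it through.** **Step 1: where a switcher falls.** The SAP has no sentence that assigns switchers to a column. Their place follows from three facts: Group 1 is defined by the Cycle 1 volume and allows for later injections; the labels in 8.5 apply to all tabulations; and no rule in section 12 refers to volume at onset or stops counting at the switch. Protocol 1.4 gives the 20 mL cohort as five patients at 4x and three at 6x, 5 + 3 = 8. Those are exactly the two 20 mL columns in 8.5, so the 20 mL block is built for the from-Cycle-1 cohort alone.

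**Step 2: reproduce the reported rates.** Protocol 1.4 gives Grade 3 or greater events as of 9/27/2022, through the 12x cohort.
- 20 mL: worsening anemia 3/8 = 37.5%; neutropenia 2/8 = 25.0%. The denominator of 8 is the from-Cycle-1 cohort, so no switcher was counted as 20 mL.
- 10 mL: worsening anemia in 4 patients, 16.7%. The only whole number from 10 to 39 that gives 16.7% is 24 (4/23 = 17.4%, 4/25 = 16.0%). The 24 is derived, not stated.

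Any switcher was therefore already on the 10 mL side of this comparison.

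**Step 3: range for incidence arising on 10 mL.** Let j be the number of the 4 anemia cases with onset after a first 20 mL injection. All 24 patients began on 10 mL, so the incidence arising on 10 mL is (4 − j)/24. The documents do not give j, so the whole range is shown.

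| j | Arising on 10 mL | Exact 95% CI |
|---|---|---|
| 0 | 4/24 = 16.7% | 4.7% to 37.4% |
| 1 | 3/24 = 12.5% | 2.7% to 32.4% |
| 2 | 2/24 = 8.3% | 1.0% to 27.0% |
| 3 | 1/24 = 4.2% | 0.1% to 21.1% |
| 4 | 0/24 = 0% | 0% to 14.2% |

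For comparison, the from-Cycle-1 20 mL rate is 3/8 = 37.5% (exact 95% CI 8.5% to 75.5%). With j = 0, Fisher's exact test of 3/8 against 4/24 gives p = 0.33.

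**Step 4: what is not affected.** Protocol 3.2.4 and SAP 8.6 base the MTD on DLTs in Cycle 1, before any switch. On the shrinkage criterion, a switch would usually follow the first scheduled scan at 6 weeks (2 × 21 = 42 days, Protocol 6.18), so early toxicity in those patients arose on 10 mL.

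**The case against.** The strongest reply is that tabulating by starting cohort is an accepted convention. Protocol 3.1.4.4 separates switchers from the cohort given 20 mL from Cycle 1, so leaving them out of the 20 mL columns follows the protocol; nothing there requires separating them from the 10 mL escalation patients. A post-switch column also has weaknesses. Switchers are selected by response or by a lesion that can no longer be injected, and they are in later cycles with more cumulative drug. Earlier polymer may persist: Protocol 1.2.1 reports about 2 months in mice, and 41% of a prototype remaining at about 2.5 months. Volume at onset therefore does not cleanly assign cause. Individual cases can already be traced through listed event dates, the dose-increase item and the tables of SQL70-related events.

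This is a good argument against replacing or truncating the starting-cohort tables. It does not answer the labelling point: a column headed by volume should say that it means starting volume, and listings are no substitute for a summary.

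Five stronger readings are tempting, and the documents do not support them:
- *That the 10 mL columns do contain 20 mL toxicity.* No section reports that anyone switched or had an event on 20 mL.
- *That crossover would push the 10 mL anemia rate above 16.7%, by mixing it with 37.5%.* The 16.7% is the observed group rate and already includes any switchers, so removing post-switch cases can only lower it. The two groups also differ in SQP33 level (0.38x to 12x against 4x and 6x).
- *That the contrast between volumes justifies the Phase 2a volumes.* The protocol bases 20 mL in Group 1 on expected tumor size (synopsis, 3.5.1) and adds a safety run-in because of that volume (3.2.7).
- *That these tables chose the RP2D.* It rests on all available data (Protocol 3.2.5), and the final tables follow database lock (SAP 7.2).
- *That SAP 11.5 needs a rule for lesions that become injected.* It specifies best change in the sum of diameters over both kinds of target lesion, with no split between them.

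**Conclusion.** The point holds as a gap in structure and labelling. As written, any adverse event or laboratory extreme arising on 20 mL after a switch would be reported under 10 mL, and at levels other than 4x and 6x no 20 mL column exists to show such experience.

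The size cannot be fixed from the documents. For the one outcome with figures, the incidence arising on 10 mL lies between 16.7% and 0%, assuming a denominator of 24 and that 0 to 4 of the 4 cases arose after a switch. If nobody switched, there is no effect. The likely direction is overstated 10 mL toxicity and a blurred contrast with 20 mL. That is not certain, because volume is mixed up with SQP33 level and time on treatment. The matter is confined to all-cycle safety summaries and is a cheap improvement to reporting, not an error shown to have changed a decision.

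**What to change.** In Phase 1 SAP 8.5 and 12:

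1. Keep the planned tables, and state that their columns give the SQL70 volume at Cycle 1 (starting cohort).
2. Derive SQL70 volume at onset for each TEAE and each post-baseline laboratory value. Add a supplementary display for patients who started on 10 mL, by SQP33 level, that separates what occurred before the first 20 mL injection from what occurred after it (10 to 20 mL, post-Cycle 1).
3. Report the number of patients who switched and the cycles given on each volume.
4. Footnote that the post-switch column is a selected, later-cycle subset with possible polymer carry-over.
5. Reconcile the cohort names: 20 mL (post-Cycle 1) in the protocol, 10 mL (post-Cycle 1) in the SAP. The SAP was written to Amendment 7, so check that wording too.

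The cost is one derived variable and one small, non-randomized table that must be read with care. SAP 10.8 and 12.1 already provide for the volume increase and the event start dates, so no new data or patients are needed. Under SAP 8.4 an added analysis calls for a SAP revision; after database lock, section 1 allows it to be described in the study report.
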